3.8 Evaluation and calculation of variables

The primary efficacy outcome measure is as follows:

- PFS (progression free survival) defined as the time from randomization to the first occurrence of disease progression (as determined using RECIST 1.1 criteria and assessed by the Investigator) or death from any cause on study. Death on study is defined as death from any cause within 30 days of the last dose of study treatment regimen. Tumor progression will be assessed locally at each site by the investigators according to RECIST 1.1. No independent review of tumor progression is planned. PFS with disease progression determined by iRECIST for patients on the combination arm will also be examined in exploratory data analysis.

The secondary efficacy outcome measures in all subjects are as follows:

- OS (overall survival) defined as the time from entry onto trial until death from any cause.
- ORR (overall response rate) defined as the subjects achieving Complete Response or Partial Response as defined by RECIST 1.1.
- CBR (clinical benefit rate) defined as subjects achieving Complete Response, Partial Response or Stable disease \geq 24 weeks

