4.8 Efficacy

The first disease evaluation for subjects following start of olaparib or olaparib in combination with durvalumab will occur at week 8 +/- 7 days. Subsequent to the first tumor evaluation, disease status and tumor response will be assessed per RECIST using standard CT/MRI scans in eight-week intervals (+/- 7 days) until disease progression as defined by RECIST 1.1 or as clinically indicated.

For subjects who discontinue any of the study drug due to toxicity in the absence of confirmed objective progression, objective tumor assessments should be continued every 8 weeks (+/- 7 days) for until confirmed objective disease progression.

If study subject is on durvalumab, disease progression requires confirmation. The confirmatory scan should occur preferably at the next scheduled visit and no earlier than 4 weeks after the initial assessment of progressive disease (PD) in the absence of clinically significant deterioration. Treatment with olaparib and durvalumab will continue between the initial assessment of progression and confirmation for progression. Subjects with rapid tumor progression or with symptomatic progression that requires urgent medical intervention (eg, central nervous system metastasis, respiratory failure due to tumor compression, spinal cord compression) will not be eligible to continue to receive study drug.

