9 APPENDICES

Appendix A : Schedule of Assessments

Extension period – please refer to sections 4.5.2 and 4.5.3 for data to be entered in eCRF.

SCHEDULE OF ASSESSMENTS					
Procedures	Screening ^p	Cycle 1 (q28)	Cycle 2 (q28) onwards	End of treatment	Follow-up
	Within 14 days	D1	D1 (+/- 3 days)	Within 30 days	Every 8 weeks (+/- 7 days)
Informed consent	X				
Inclusion/exclusion criteria check	X				
Demographics	X				
Past medical history including past cancer chemotherapy, radiotherapy and surgery	X				
Archival tumor tissue sample	X ^b				
Tumor assessment (CT or MRI) ^c	X		X ^d		X ^d
Complete physical examination	X	X	X	X	
Weight (with height at screening)	X	X	X		

Vital signs ^e	X	X ^e	X ^e	X	
AE and toxicities	X	X	X	X ^f	
Concomitant medications	X	X	X	X	
ECOG performance status	X	X	X	X	
Hematology ^g	X	X ⁿ	X	X	
Chemistry and electrolyte ^h	X	X ^o	X	X	
Liver panel (ALT/AST/Bilirubin) ⁱ	X	X ⁿ	X	X	
GFR assessment ^j	X	X ⁿ	X	X	
Pregnancy test ^k	X				
Buccal Swab for DNA analysis	X				
Biomarker blood tests ^l		X	X [after staging, at alternating Cycles 3,5,7, etc]	X	
Optional tumor biopsy ^m	X ^l			X ^m	
If CR/PR/SD:					
Randomization	X				
Olaparib		300 mg BID daily			
If randomized to combination arm:					
Durvalumab IV 1500 mg		X	X		
Survival assessment ⁿ					X ⁿ

NOTE: Results of standard-of-care tests or examinations performed prior to obtaining informed consent but within the screening window (Day-14 to Day -1) may be used for the study. Investigations, such as CT or MRI scans that have been performed as part of routine clinical practice to assess response to platinum, can be used as part of the screening process if performed within 28 days of first dose of study treatment. Screening assessments are to be performed within 14 days preceding cycle 1 day 1 unless otherwise noted. Except for cycle 1 day 1, all other study visits and assessments during the treatment period should be performed within +/- 3 days of the scheduled date. Study assessments may be delayed or moved ahead of the window to accommodate holidays, vacations and unforeseen delays. All assessments and procedures to be performed pre-dose unless otherwise specified.

^a The end of treatment visit should occur approximately 30 days after the last administration of olaparib or durvalumab

whichever is discontinued last, or until initiation of another therapeutic regimen.

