^b Archival tissue (either formalin fixed paraffin embedded tumor specimens or a minimum of 10 unstained paraffin slides) must be available prior to entry into the study. In the absence of archival tissue, fresh tissue biopsy samples, excluding cytology and fine needle aspiration specimens are acceptable.

^c Tumor assessments performed according to RECIST version 1.1 The method used for a patient (CT or MRI) must be the same throughout the study.

^d Tumor assessment performed every 8 weeks starting on Days 21-28 of Cycle 2 and every 8 weeks (+/- 7 days) thereafter until documented disease progression. The results should be reviewed prior to dosing at the next cycle; tumor assessments should be performed <=7 days prior to continuation of study treatment on Day 1 of the subsequent cycle.

^e Includes heart rate, systolic and diastolic blood pressure whilst in a seated position, and temperature. On durvalumab dosing days, recorded prior to dosing and at the end of the infusion.

^f Patients with unresolved adverse events or serious adverse events will be followed until the event is resolved or stabilized, the patient is lost to follow-up or it has been determined that the study treatment or participation is not the cause of the event.

^g Includes RBC count, WBC count, WBC differential count (neutrophils, bands, lymphocytes, eosinophils, basophils, monocytes and other cells), absolute neutrophil count, hemoglobin, hematocrit and platelet count.

^h Includes sodium, potassium, chloride, bicarbonate urea, creatinine, calcium, phosphorus, magnesium, thyroid stimulating hormone (combination arm only), free triiodothyronine (T3) (combination arm only) and free thyroxine (T4) (combination arm only). See Appendix G for additional required tests for Korean sites only.

ⁱ Includes total bilirubin, total protein, albumin, AST, ALT and alkaline phosphatase.

^j As calculated by the Cockcroft-Gault formula.

^k For women of childbearing potential (including those who have had a tubal ligation). For all other women, documentation must be present in medical history confirming the patients is not of childbearing potential.

^l Biomarker blood specimens will be collected at visit C1D1, D1 after each staging cycle (C3D1, C5D1, C7D1 etc), and End of Treatment (EOT).

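### Tumor scans are set by calendar week in section 4.8 but by dosing cycle in Appendix A, so a delayed cycle could postpone the scan and lengthen measured PFS

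*Combined protocol and SAP*

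**What the plan says.** Section 4.8 (Efficacy) starts its clock at the first dose of study treatment. The first disease evaluation "will occur at week 8 +/- 7 days", and later ones follow at eight-week intervals with the same 7-day tolerance.

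Appendix A, footnote d, uses the dosing cycle: "Tumor assessment performed every 8 weeks starting on Days 21-28 of Cycle 2", then "every 8 weeks (+/- 7 days) thereafter until documented disease progression". It adds that "tumor assessments should be performed <=7 days prior to continuation of study treatment on Day 1 of the subsequent cycle".

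The general note to Appendix A sets a further tolerance: "all other study visits and assessments during the treatment period should be performed within +/- 3 days of the scheduled date". It then relaxes it: "Study assessments may be delayed or moved ahead of the window to accommodate holidays, vacations and unforeseen delays".

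PFS uses neither scan clock. Section 3.8 has it "defined as the time from randomization to the first occurrence of disease progression" or death on study, and section 4.8.1 repeats this.

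Section 4.2.4 allows olaparib interruptions of up to 14 days per occasion, and of up to 4 weeks for grade 3 or worse hematological toxicity. No section says whether a hold postpones Day 1 of the next cycle, or which scan rule governs if it does.

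**The concern.** Progression by imaging is normally dated at the scan that shows it, so a later scan gives a longer PFS for the same disease course. Section 7.1 tests each arm alone against a fixed median of 2 months, about 61 days. Randomization balances the arms against each other but does not protect a single-arm test from scans that run late in that arm.

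The two rules respond differently to a delayed cycle. The 4.8 date stays where it is. Both parts of footnote d can move: a late Cycle 2 moves its Days 21-28, and a late Cycle 3 Day 1 moves the 7-day limit before it. Delay caused by toxicity would then count as apparent benefit on the primary endpoint, by an amount that depends on which part of the protocol a site follows.

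**Working it through.** **Plan's own figure.** Section 7.1 gives 25 subjects per arm (median 2 v 4 months, exponential MLE test, two-sided 5%, 90% power). On the log scale the events needed are ((1.960 + 1.282)/ln 2)² = 21.9. Dividing by an event fraction of 0.875, which is 12 months of follow-up for everyone at a 4-month median (1 − 0.5^(12/4)), gives 25.0. Follow-up is not stated, so 25 is plausible but cannot be confirmed. The check below uses n = 25 with every progression observed.

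**Windows without delay.** Section 4.8: 56 ± 7 gives days 49-63. Footnote d with a 28-day Cycle 1: 28 + 21 to 28 + 28 gives days 49-56. The second lies wholly inside the first, so the rules differ only on days 57-63 of the first scan. Later scans are every 8 weeks ± 7 days in both.

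**Windows if Cycle 2 starts late.**

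| Slip | Footnote d | Shared with days 49-63 |
|---|---|---|
| 7 days | 56-63 | all |
| 14 days | 63-70 | day 63 only |
| 28 days | 77-84 | none |

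**Effect on the test at a true median of 2 months.** With 30.4375 days per month, true times t are exponential with mean 2 × 30.4375/ln 2 = 87.8 days. With first scan on day f, progression is dated at f + 56 × max(0, ⌈(t − f)/56⌉). The estimated median is m = ln 2 × (mean dated time)/30.4375.

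Section 7.1 does not say which form of the exponential MLE test applies. Favourable rejection (nominal upper tail 2.5%) needs:

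- log scale: √25 × ln(m/2) > 1.96, so m > 2e^0.392 = 2.96 months
- exact chi-square on 50 degrees of freedom: m > 2 × 71.42/50 = 2.86 months
- Wald on the mean scale: (m − 2)/(m/5) > 1.96, so m > 2/(1 − 0.392) = 3.29 months

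Simulated rejection with the log-scale test:

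| First scan | Favourable rejection |
|---|---|
| Spread evenly over footnote d window (49-56) | 23.3% |
| Spread evenly over 4.8 window (49-63) | 24.7% |
| All on day 56 | about 23% |
| Day 56, 20-40% of subjects slip 14 days | 25-27% |
| Day 56, 20-40% of subjects slip 28 days | 27-31% |

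The difference in windows alone is 24.7 − 23.3 = 1.4 points. Relative to day 56, 14-day slips add about 2-4 points and 28-day slips about 4-8. Across both slip lengths the exact test goes from 31% to 34-40%, and the mean-scale Wald test from about 8% to 8-11%. The direction is the same in all three.

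**Assumptions not in the documents:** the 20-40% slip rate, no deaths or unscheduled scans between visits, no censoring, and no lag from randomization to first dose.

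**The case against.** The strongest reply is that the rules do not conflict as written. A site that keeps to footnote d with no delay also meets 4.8, and later scans carry the same interval and tolerance. This stands.

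A reader might set everyone scanned on day 49 against everyone scanned on day 63 (21% v 30% favourable rejection, log-scale test) and attribute 9 points to the discrepancy. That does not follow. Day 49 satisfies both rules, days 49-63 are 4.8's own window, and no site would put all its subjects at one extreme. With scans spread over each window the difference is about 1.4 points.

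Drift through dose holds is also inferred. Section 4.2.2 describes continuous dosing in 28-day cycles, section 4.5.2 sets visits every 28 ± 3 days, and nothing says that a hold postpones Day 1. The slip rate has no source. Section 4.1.5 permits scans whenever progression is suspected, and deaths on study count as events; both would reduce the lateness. These points limit the size. They do not remove the gap, because footnote d refers to treatment continuing on Day 1 and the protocol does not say what happens when it does not continue on time.

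A reader might also infer that one arm is favoured over the other. The documents do not say which arm would have more holds, and the between-arm comparison is exploratory.

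**Conclusion.** The point holds as a gap in the scan schedule, not as a direct contradiction. The protocol does not say whether a delayed cycle moves the scan, and its two rules give different answers. If cycles do slip, the bias is upward, depends on toxicity, and enters each arm's primary test. Under the assumptions stated, it adds about 2-8 points to favourable rejection on the log-scale test. The level varies with the test form, which section 7.1 leaves open.

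It would be wrong to read the 23% starting level as a result of the two clocks. Most of it comes from scanning every 8 weeks against a 2-month null, and reconciling the two passages will not remove it. Nor does a first scan after day 61 decide the result by itself: the exponential MLE test uses total follow-up time over events, not whether each progression is dated beyond 2 months. The case for the change is that it removes an avoidable influence on the primary endpoint at very little cost.

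**What to change.** Give section 4.8 and footnote d the same rule: tumor assessments every 8 weeks +/- 7 days, counted in calendar weeks from randomization (the PFS origin), and not moved by dose holds or cycle delays. Remove the Cycle 2 anchor from footnote d, and make the limit of 7 days before the next Day 1 subordinate to the calendar date. State that the general 3-day window and the allowance for moving assessments in the Appendix A note do not apply to tumor scans.

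This leaves the scan frequency and every dosing rule as they are. The cost is wording, plus some scans that will not line up with a dosing visit when a cycle is delayed.

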Appendix B : Known Strong in Vivo Inhibitors or Inducers of CYP3A

Strong Inhibitors of CYP3Aa	Strong Inducers of CYP3Ae
Boceprevir	carbamazepin ^{ef}
clarithromycin ^b	phenytoin ^f
conivaptin ^b	rifampin ^f
grapefruit juice ^c	St John's wort ^f
indinavir	
itraconazoleb	
ketoconazoleb	
lopinavir/ritonavir ^b (combination drug)	
mibefradil ^d	
nefazodone	
nelfinavir	
posaconazole	
ritonavir ^b	
saquinavir	
telaprevir	
telithromycin	
voriconazole	

Source:

FDA Drug Development and Drug Interactions: Table of Substrates, Inhibitors and Inducers. Web link Accessed 21 January 2015:

<http://www.fda.gov/Drugs/DevelopmentApprovalProcess/DevelopmentResources/DrugInteractionsLabeling/ucm093664.htm#inVivo>

Note: The list of drugs in these tables is not exhaustive. Any questions about drugs not on this list should be addressed to the Study Chair of the protocol.

a. A strong inhibitor for CYP3A is defined as an inhibitor that increases the AUC of a substrate for CYP3A by ≥ 5 -fold.

b. In vivo inhibitor of P-glycoprotein.

c. The effect of grapefruit juice varies widely among brands and is concentration-, dose-, and preparation-dependent. Studies have shown that it can be classified as a “strong CYP3A inhibitor” when a certain preparation was used (eg, high dose, double strength) or as a “moderate CYP3A inhibitor” when another preparation was used (eg, low dose, single strength).

d. Withdrawn from the United States market because of safety reasons.

e. A strong inducer for CYP3A is defined as an inducer that results in $\geq 80\%$ decrease in the AUC of a substrate for CYP3A.

f. In vivo inducer of P-glycoprotein.

Appendix C : Adverse Event Assessment of Causality

Is there a reasonable possibility that the event may have been caused by study drugs? No___ Yes___

The descriptions provided below will help guide the principal investigator in making the decision to choose either “yes” or “no”:

No = There is no reasonable possibility that the event may have been caused by study drugs.

The adverse event:

- may be judged to be due to extraneous causes such as disease or environment or toxic factors
- may be judged to be due to the subject’s clinical state or other therapy being administered
- is not biologically plausible
- does not reappear or worsen when study drug is re-administered
- does not follow a temporal sequence from administration of study drug

Yes = There is a reasonable possibility that the event may have been caused by study drugs.

The adverse event:

- follows a temporal sequence from administration of study drug
- is a known response to the study drug based on clinical or preclinical data
- could not be explained by the known characteristics of the subject’s clinical state, environmental or toxic factors, or other therapy administered to the subject
- disappears or decreases upon cessation or reduction of dose of study drug
 - reappears or worsens when study drug is re-administered

Appendix D : Under 30 kg Total Body Weight Durvalumab Dose calculation

Dose Calculations ONLY for subjects 30kg body weight and under. ALL subjects over 30kg total body weight are given fixed dosing of 1500mg every 4 weeks (see section 1.5.2)

1. Ordered dose: 20 mg/kg
2. Subject weight: X kg
3. Dose for subject: $Y \text{ mg} = 20 \text{ (mg/kg)} \times X \text{ (kg)}$
4. Dose to be added into infusion bag:

Dose (mL) = $Y \text{ mg} / 50 \text{ (mg/mL)}$ where 50 mg/mL is durvalumab nominal concentration.

The corresponding volume of durvalumab should be rounded to the nearest tenth mL (0.1 mL).
Dose adjustments for each cycle are only needed for greater than 10% change in weight.

5. The theoretical number of vials required for dose preparation is the next greatest whole number of vials from the following formula:

Number of vials = $\text{Dose (mL)} / 10.0 \text{ (mL/vial)}$

Example for 30kg subject dosing at 20mg/kg every 4 weeks:

1. Ordered dose: 20 mg/kg every 4 weeks
2. Subject weight: 30 kg
3. Dose for subject: $600 \text{ mg} = 20 \text{ (mg/kg)} \times 30 \text{ (kg)}$
4. Dose to be added into infusion bag: $\text{Dose (mL)} = 600 \text{ mg} / 50 \text{ (mg/mL)} = 12.0 \text{ mL}$
5. The theoretical number of vials required for dose preparation:

Number of vials = $12.0 \text{ (mL)} / 10.0 \text{ (mL/vial)} = 2 \text{ vials}$

(provided by Astra Zeneca)

Appendix E : Assessment of Possible Drug Induced Liver Injury

The following assessments are to be reported in the clinical database, utilizing Comment Form as necessary for additional information.

- Subject's age, sex, weight, and height
- Signs and symptoms related to hepatotoxicity: type and timing to exposure
- Relationship of exposure duration and dose to the development of the liver injury
- Pertinent medical history • Concomitant drugs with dates and doses • Pertinent physical exam findings
- Test results (e.g., laboratory data, biopsy data and reports, with dates and normal ranges)
- Time course of serum enzyme and bilirubin elevations (consider tabular and/or graphical display of serial laboratory data)
- A summary of all available clinical information including, if known:
 - Prior or current history of ethanol use
 - Presence of risk factors for NASH (e.g., obesity, diabetes, marked hypertriglyceridemia) 16 Contains Nonbinding Recommendations
 - Evidence for pre- or co-existing viral hepatitis, or other forms of liver disease, prestudy AT values, if available
 - Symptoms and clinical course including follow-up to resolution – Special studies (i.e., ultrasound, radiologic examinations, liver biopsy results)
 - Presence or absence of possible confounders, including concomitant illness, use of concomitant drugs that are known hepatotoxins, such as acetaminophen
- Treatment provided
- Dechallenge and rechallenge results, if done
- Outcomes and follow-up information
- The site should also supply redacted copies of available hospital discharge summaries, pathology and autopsy reports

Appendix F : Toxicity Management Guidelines Durvalumab

These guidelines are now provided to sites as a separate document.

Appendix G : Additional required tests (Korean sites ONLY)

4.1.2 Screening Procedures

- 12 lead resting ECG
- Amylase, Lipase, GGT (gamma glutamyl transferase), Urinalysis

4.5.1 During olaparib or olaparib and durvalumab maintenance

- Amylase, Lipase
- As clinically indicated: GGT, Urinalysis

4.5.2 Subsequent visits (and Table 7. Clinical chemistry Serum or Plasma Laboratory Tests)

- Amylase, Lipase
- As clinically indicated: GGT, Urinalysis

Urinalysis Tests^a

Bilirubin

Blood

Glucose

Ketones

pH

Protein

Specific gravity

Colour and appearance

^a Microscopy should be used as appropriate to investigate white blood cells and use the high power field for red blood cells
